## 8.0 Reportable Events

There are no additionally anticipated risks or adverse reactions by using 2% Lidocaine w/ 1:100k epi, 3% carbocaine without epi and 4% septocaine with 1:100k epi plane or with a sodium bicarbonate buffer as compared to a traditional, non-buffered formulation of the same local anesthetic. However, potential adverse events involving the traditional method of administering local anesthetic for mandibular teeth may involve hematomas, a temporary increase in heart rate, needle tract infections, temporary nerve damage (including Bell's Palsy), and an inadequate

anesthetic delivery/lack of efficacy. Serious adverse events relating to local anesthetics may include overdose (drowsiness/loss of consciousness), permanent nerve damage, allergic reactions/anaphylaxis, or exacerbation of an underlying cardiovascular condition due to the presence of exogenous epinephrine.

## **9.0 Data Safety Monitoring**

The PI and student PI will be responsible for the data and safety monitoring. They will monitor data quality, subject recruitment, accrual, retention, outcome and adverse event data, assessment of scientific reports or therapeutic development, results of related studies that may impact subject safety, and procedures designed to protect the privacy of subjects. Safety data will be monitored on a regular basis and immediately upon discover of any SAE or major study event or protocol deviation.

## **10.0 Study Withdrawal/Discontinuation**

A subject may withdraw from the study for any reason and at any time during the study without penalty. There dental treatment will not be affected by their decision to stop study related procedures. The Principal Investigator may also withdraw the subject if he feels study participation is not safe for the study to continue, or if the subject is not cooperating with study procedures.

## **11.0 Statistical Considerations**

The two groups will be compared for differences in the percentage of subjects who fail to achieve profound pulpal anesthesia using chi-square tests. The time needed to achieve profound pulpal anesthesia for the two groups will be compared using Kaplan-Meier survival curves and log-rank tests, with patients who fail to achieve profound pulpal anesthesia censored at 15 minutes. A logistic regression model for presence of profound pulpal anesthesia will be used to determine whether molar type (first, second, third molar) affects the group comparisons; the model will include both factors and their interaction. A similar Cox proportional hazards survival model will be used for the analysis of time needed to achieve profound pulpal anesthesia. VAS scores will be compared between treatments using a Wilcoxon Rank Sum test. A two-sided 5% significance level will be used for all tests.

With a sample size of 28 subjects per group, the study will have 80% power to detect a hazard ratio of 2.25 between the two groups for time to profound pulpal anesthesia, using calculations with a two-sided 5% significance level and based on a log-rank test with median time to anesthesia 10 minutes in the control group. Sample size calculations were performed using PASS 2019 (NCSS, LLC. Kaysville, UT). To account for up to 2 subjects per group with unusable data, the study will enroll 30 subjects per group.

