### **1.0 Background & Rationale**

---

The success rate for pulpal anesthesia in mandibular molars diagnosed with symptomatic irreversible pulpitis has been shown to be between 45-70% (1). While the specific mechanism for inadequacy is unknown, it has been proposed that expression of variable sodium channels during inflammation, changes in tissue pH and, peripheral blood flow may contribute (2). OnPharmaTM offers a solution to increase the efficacy of local anesthetics by allowing the clinician to add a buffering agent to the solution prior to injection.

The OnPharmaTM system adds sodium bicarbonate to the anesthetic solution to raise its pH to a level closer to the anesthetics pKa. In doing so, more of the free base form is present to

diffuse through cell membranes. The free base is the active ingredient in local anesthetic solutions that are responsible for analgesia. In addition, CO2 and water are produced through the addition of sodium bicarbonate to the anesthetic solution. CO2 converts the local anesthetic back into its active acid form once inside the cell membrane, trapping the local anesthetic inside (2,3).

Recent studies have suggested that buffered anesthetics do not improve Inferior alveolar nerve block (IANB) success rate in symptomatic teeth (4,5,6). This contrasts with another study showing increased success with sodium bicarbonate use with IANB blocks (7). While the field is not currently in agreement, Indiana University School of Dentistry (IUSD) has had a positive experience when using the OnPharmaTM system to anesthetize symptomatic teeth.

[name], a previous resident of Indiana University Endodontics, investigated the efficacy of buffered and plain 2% lidocaine with 1:100k epinephrine. His data suggest that there is not a significant difference between the two when treating mandibular molars diagnosed with symptomatic irreversible pulpitis. This current iteration aims to investigate the synergistic ability of a combination of buffered anesthetics to improve patient analgesia. Previous studies have reported that a local infiltration of articaine with a IANB of lidocaine improve local anesthetic success rates in patients diagnosed with symptomatic irreversible pulps (8,9). Carbocaine performs as well as lidocaine when used solely for an IANB but current data suggests it does not improve anesthesia when combined with other anesthetics (10,11).

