**3.0      Outcome Measures/Endpoints**

**3.1      Primary Outcome Measures**

**3.1.1** The primary outcome is to gauge the time it takes for the buffered anesthetic to provide profound anesthesia, displayed by an EPT reading of 80. The time will be censored at 15 minutes if profound anesthesia is not achieved within 15 minutes.

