### **4.2 Exclusion Criteria**

- Patients lacking a response to cold in the affected tooth
- A radiographic periradicular pathosis more advanced than a widened periodontal ligament (radiograph taken as standard of care)
- No vital coronal pulp tissue noted upon access
- Patient reported pain (other than pressure) upon endodontic access/pulpotomy

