7. Administer **1 carpule** (1.8mL) of the previously determined formulation of 2% Lidocaine w/ 1:100k epi and 1 carpule of 3% Carbocaine plane via IANB, followed by 0.5 carpules (0.9mL) of 4% Septocaine with 1:100k epi via buccal infiltration and 0.5 carpules of 4% Septocaine with 1:100k epi via lingual infiltration (about 3 minutes)
8. Using a stopwatch, the student researcher will wait 3 minutes after administering anesthesia and then obtain the 2nd EPT reading on the tooth being treated, as well as assessing soft tissue anesthesia of the respective side of the mandible

- a. EPT=80 (maximum stimulation) without pulpal or soft tissue sensations indicates profound pulpal anesthesia and the endodontic access may be initiated
- b. EPT $\neq$ 80 with pulpal and/or soft tissue sensations indicates a need to wait additional time
9. Retest the tooth being treated using EPT at 2-minute intervals until EPT=80 or when 15 minutes have passed
  - a. Participants who did not demonstrate total soft tissue and/or pulpal anesthesia within 15 minutes will be categorized as a failure (lack of anesthetic profoundness), with time to anesthesia censored at 15 minutes. No additional study outcomes will be collected from the patients, who will be withdrawn from the study, and further managed according to the best clinical practice (additional block/supplementary injections) so that the endodontic treatment may continue appropriately
10. Patients who indicate any pain (excluding pressure) elicited from the tooth undergoing treatment upon endodontic access or a complete pulpotomy (after initially confirming pulpal anesthesia with the EPT) will also be categorized as a failure (lack of anesthetic profoundness), withdrawn from the study, and appropriately managed as previously described.
  - a. Visual Analog Scales (VAS) shown below will be used to report the patient's perceived discomfort at the end of treatment.

11. The student researcher will chart the data for each uniquely identified study participant regarding the initial EPT readings (treated tooth and control), the amount of time taken to reach both soft tissue and pulpal anesthesia, and the conditions that lead to a "failed" profoundness of anesthesia
  - a. A trained research assistant will separately record each patient's unique identifying code with the anesthetic formulation (buffered vs. unbuffered) that was prepared and administered

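### Minor: the group-by-molar models have no sparse-cell method or named interaction test, though under the sample-size assumptions a zero or empty cell is likely in the logistic model (81/78% at 28/30 per arm, equal molar thirds)

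*Combined protocol and SAP*

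**What the plan says.** Section 11.0 assigns the molar-type question (secondary objective 2.2.1) to a logistic model for presence of profound anesthesia. Its factors are treatment group and molar type (first, second, third), and "the model will include both factors and their interaction". A similar Cox model is planned for time to anesthesia. The section sets a two-sided 5% level for all tests. It does not say how the interaction is tested, how sparse cells are handled, or what happens if a cell is empty. Section 6.0 describes block randomization and states no stratification by molar type.

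The figures that determine how sparse the cells will be are also in the plan:

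- Section 11.0: with 28 per group, "the study will have 80% power to detect a hazard ratio of 2.25 between the two groups", based on a "median time to anesthesia 10 minutes in the control group"; 30 per group are enrolled.
- Section 3.1: "The time will be censored at 15 minutes if profound anesthesia is not achieved within 15 minutes".
- Section 7.0, step 9: "Participants who did not demonstrate total soft tissue and/or pulpal anesthesia within 15 minutes will be categorized as a failure".
- Section 7.0, step 10: patients with pain on access or pulpotomy "will also be categorized as a failure (lack of anesthetic profoundness), withdrawn from the study".
- Section 4.2 lists the same event as an exclusion: "Patient reported pain (other than pressure) upon endodontic access/pulpotomy".
- Section 1.0, background rate in per cent: "The success rate for pulpal anesthesia in mandibular molars diagnosed with symptomatic irreversible pulpitis has been shown to be between 45-70".

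**The concern.** The logistic model has six parameters for six cells, so each interaction odds ratio rests on single cell counts. If treatment works as well as the sample size assumes, few buffered patients fail, and those few failures are spread over three molar types. A cell with no failures, no successes or no patients leaves the odds ratios that use it without a finite maximum-likelihood estimate. The test then matters: a Wald test is nearly powerless in that situation, while a likelihood-ratio test stays finite. Because the plan leaves the test open, it could be chosen after the data are seen. The cost falls on one secondary objective, where a non-significant Wald result would say little about whether molar type matters.

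**Working it through.** **The plan's own figure.** With exponential times and no cut-off, let λ0 = ln2/10 = 0.0693, λ1 = 2.25·λ0 = 0.1560 and λ̄ = 0.1126. Power = Φ{[√28·(λ1−λ0) − 1.96·√2·λ̄] / √(λ0²+λ1²)} = Φ{(0.4585 − 0.3122)/0.1707} = 80.4%. The stated 80% is reproduced, which supports reading the inputs as exponential. The same formula with the 15-minute cut-off gives 72.8%; that is a separate matter and does not affect this point.

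**Failures by 15 minutes.**
- Control success: 1 − exp(−1.5·ln2) = 64.6%.
- Buffered success: 1 − exp(−2.25·1.5·ln2) = 90.4%.
- Expected buffered failures: 28 × 0.0964 = 2.70, or 30 × 0.0964 = 2.89, over three molar types.

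**Chance of a zero or empty cell.** Each arm is multinomial over six categories (three molar types by success or failure). The probability that all six are non-zero follows by inclusion-exclusion, and the risk is 1 minus the product over arms. With 28 per arm and equal thirds, the risk is 9.1% in the control arm and 79.4% in the buffered arm, so 1 − 0.909 × 0.206 = 81%. With 30 per arm it is 78%.

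The documents give no molar mix and no access-pain rate; both are assumed below. Entries are per cent at 28/30 per arm, by third-molar share.

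| Scenario | one third | 15% | 10% | 5% |
|---|---|---|---|---|
| HR 2.25, EPT failures only | 81/78 | 89/87 | 95/93 | 99/99 |
| plus 5% of EPT successes failing | 63/58 | 78/75 | 89/87 | 98/97 |
| plus 10% | 46/41 | 68/63 | 83/80 | 97/96 |
| plus 15% | 32/27 | 59/54 | 78/75 | 96/95 |
| No treatment effect | 17/14 | 48/43 | 73/69 | 95/94 |
| 55% v 70% success | 19/15 | 49/44 | 73/69 | 95/94 |

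With Weibull shape 0.75 or 1.5 instead of exponential (HR 2.25, equal thirds), the risk is 71/67% or 95/93%.

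**Cox model.** Here the trouble is a cell with no events (no successes by 15 minutes). At HR 2.25 the probability is under 1% with equal thirds, and 7/6%, 21/19% and 56/53% with 15%, 10% and 5% third molars. For example, at 10% and 28 per arm the third-molar cells alone give 1 − (1 − 0.935^28)(1 − 0.910^28), about 21%.

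**Interaction tests.** Simulated rejection at the 5% level, 28 per arm, equal thirds, control success 64.6% in each molar type. Buffered success by molar type is assumed. The Wald figures set zero-cell logits at ±20, as after 20 fitting steps.

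| Buffered success | Wald | Ordinary likelihood-ratio | Penalized likelihood-ratio |
|---|---|---|---|
| No interaction, HR 2.25 | 0.1% | 6.0% | 1.7% |
| No interaction, no treatment effect | 1.9% | 8.4% | 4.4% |
| 98/98/45% | 2.4% | 66% | 43% |
| 90/90/45% | 7.3% | 43% | 28% |
| 97/97/77% (keeps the 90.4% average) | 0.2% | 18% | 6.6% |

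**The case against.** The 81/78% figure rests on EPT failures only, yet Section 7.0 also counts access pain and missing soft-tissue anesthesia as failures. With equal thirds, the risk drops below 50% once these take 9% (28 per arm) or 8% (30 per arm) of EPT successes. This stands: the figure is conditional. A reader might infer that the model will break down in most trials whatever happens, and the documents do not support that. Nor do they support treating equal thirds as a worst case: among the mixes examined it is the most favourable.

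The plan never specifies a Wald test, and the ordinary likelihood-ratio test stays finite with a zero cell. Its false rejection is close to nominal (about 6%) at HR 2.25, and it has more power than the penalized test. This also stands. A reader might infer that a penalized test is required; that would be a preference. But a likelihood-ratio test does not supply finite odds ratios, and the plan does not name one.

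Two of the assumed interactions put buffered success below control in one molar type (45% v 64.6%), which nothing in the documents suggests. They show how the tests differ and are not predictions. Very large standard errors would often be visible in the output, which limits the harm but is not a pre-specified rule.

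A reader might also infer that only the profoundness half of objective 2.2.1 is touched. The Cox figures show that the time half is exposed too when third molars are few.

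**Conclusion.** The point holds as a minor, cheap improvement to one secondary objective. Under the sample-size assumptions, with exponential times, equal thirds and EPT failures only, the ordinary logistic interaction fit has an 81/78% chance of a zero or empty cell. That becomes 32/27% with 15% further failures and 17/14% with no treatment effect, but 73/69% even with no effect if third molars are 10%. The molar mix and the rate of further failures are unknown, so the plan cannot show that the risk is small. A Wald test would miss even an extreme interaction (about 2% v 66% for the ordinary likelihood-ratio test). No test has good power for a moderate interaction (at most 18% at 97/97/77%), so the intervals matter more than the p-value. The primary log-rank test and the chi-square and rank-sum comparisons of the two groups do not depend on these models, and it would be wrong to read this as a weakness in them.

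**What to change.** Add to Section 11.0, in words such as these:

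- Interaction odds ratios in the logistic model will be estimated by Firth penalized likelihood, with profile penalized-likelihood 95% intervals.
- The interaction will be tested by one pre-specified likelihood-ratio test (state which: penalized or ordinary), with 2 df or fewer if a contrast is not estimable, and not by a Wald test.
- Patients and failures will be tabulated for each of the six cells.
- In both the logistic and the Cox model, if a group-by-molar cell has no patients (or, for Cox, no events), third molars will be pooled with second molars for the interaction test (1 df) and the third-molar contrast reported as not estimable.

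The cost is a few sentences, with no change to design, sample size or data collected. There are downsides. Penalized estimates are shrunk. The penalized test is conservative (about 1.5% false rejection at HR 2.25) and less powerful, while the ordinary test rejects falsely in about 8% of trials with no treatment effect. For the logistic model with pooling, the penalized test's false rejection stayed at 1.5 to 4.5% over 24 simulated settings without interaction. The Cox pooling trigger depends on outcomes, and its effect on that test was not simulated. Empty cells would trigger pooling in about 0% of trials with equal thirds, 2% with 15% third molars, 8–10% with 10% and 38–42% with 5%.

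Separately, Sections 4.2 and 7.0 treat pain on access differently. They must be reconciled first, and Section 11.0 should then state which failure definition the logistic model uses.

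### The stated 80% power at 28 per group does not follow from a 10-minute control median and 15-minute censoring under exponential times; it is about 76%, and about 79% at 30 per group.

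*Combined protocol and SAP*

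**What the plan says.** Section 11.0 bases the sample size on the primary endpoint, time to profound pulpal anesthesia: "With a sample size of 28 subjects per group, the study will have 80% power to detect a hazard ratio of 2.25". The calculation is "based on a log-rank test with median time to anesthesia 10 minutes in the control group", two-sided at 5%, run in PASS 2019. Enrollment is set at 30 per group to allow for up to 2 per group with unusable data.

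The plan applies a 15-minute limit in three places:

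- Section 3.1: "The time will be censored at 15 minutes if profound anesthesia is not achieved within 15 minutes".
- Section 7.0, step 9: "Retest the tooth being treated using EPT at 2-minute intervals until EPT=80 or when 15 minutes have passed".
- Section 11.0, in the description of the survival analysis: "with patients who fail to achieve profound pulpal anesthesia censored at 15 minutes".

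The power statement itself gives no follow-up time, time distribution, expected proportion with an event, or number of events. It also does not name the PASS procedure.

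**The concern.** Log-rank power depends on the number of events, not the number of subjects. With a control median of 10 minutes and observation ending at 15, a sizeable share of controls will be censored. A median and a hazard ratio with no other curve information are the usual inputs for an exponential calculation. Under that reading, 56 subjects do not yield enough events for 80% power.

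This is the only justification given for the sample size. If the figure is too high, a null result would be read against a power the design may not have: a type II error of about 24% at HR 2.25 rather than 20%. As written, a reader also cannot see that 80% depends on an undisclosed control curve, or tell whether the 15-minute limit was entered in the calculation.

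**Working it through.** **Inputs.** From Section 11.0: n = 28 per group, HR = 2.25, two-sided alpha 0.05, control median 10 minutes. From Sections 3.1, 7.0 and 11.0: follow-up ends at 15 minutes. From Section 6.0: equal allocation. My assumption: exponential times.

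**Can the plan's 80% be reproduced?** Not with 15-minute censoring and exponential times. Other settings do return it at 28 per group:

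- Schoenfeld with follow-up of 20 minutes: 47.8 events, 80.0%.
- Lachin-Foulkes hazard-difference form with no censoring: 79.1% at 27 per group, 80.4% at 28.

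Uncensored Schoenfeld gives 85.9% and uncensored Freedman 82.1%. Since more than one setting matches, the origin of the figure cannot be identified.

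**Events by 15 minutes.**

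- Control: 1 − exp(−15·ln2/10) = 0.6464
- Buffered: 1 − exp(−2.25·15·ln2/10) = 0.9036
- Expected events: 28 × (0.6464 + 0.9036) = 43.4

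**Events needed for 80% power (Schoenfeld).** 4·(1.96 + 0.8416)² / (ln 2.25)² = 47.7.

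**Power.** Φ(√(D/4)·ln 2.25 − 1.96), where D is the expected number of events:

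- 28 per group, D = 43.4: 76.2%
- 30 per group, D = 46.5: 79.0%
- 31 per group, D = 48.1: 80.3%

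80% power at 28 per group needs HR ≈ 2.34.

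**Simulation.** Log-rank tests, 40,000 trials per cell, with continuous times and with events recorded on the 3, 5, …, 15-minute testing grid:

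| n per group | HR | Continuous | Grid |
|---|---|---|---|
| 28 | 2.25 | 75.7% | 75.7% |
| 30 | 2.25 | 79.0% | 78.8% |
| 28 | 2.35 | 80.3% | 80.1% |

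**Other formulas**, 28 per group with 15-minute censoring: Lakatos 75.8%, exponential log-hazard-ratio test 75.0%, Lachin-Foulkes 72.8%, Freedman 71.7%. None comes within 2 points of 80%.

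**Dependence on the curve.** Weibull times with the same median and HR have control cumulative hazard ln2·1.5^k at 15 minutes. Schoenfeld power:

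| Shape k | Controls with event by 15 min | Power, 28 per group | Power, 30 per group |
|---|---|---|---|
| 0.75 | 60.9% | 74.5% | 77.3% |
| 1.0 | 64.6% | 76.2% | 79.0% |
| 1.25 | 68.4% | 77.7% | 80.4% |
| 1.5 | 72.0% | 79.0% | 81.7% |
| 1.75 | 75.6% | 80.2% | 82.8% |
| 2.0 | 79.0% | 81.2% | 83.8% |

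**Without naming a distribution.** Under proportional hazards the buffered event proportion is 1 − (1 − p)^2.25, where p is the control proportion by 15 minutes, so Schoenfeld power depends only on p and n. Reaching 80% requires p = 74.9% at 28 per group or 67.3% at 30.

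**The case against.** The strongest reply is that no contradiction has been proved. A median does not fix the proportion of controls anesthetized by 15 minutes, so the stated inputs do not determine a power; the exponential curve is supplied from outside. It implies that about 19% of controls are already anesthetized at the first reading at 3 minutes, which the plan neither supports nor excludes. A delayed onset narrows the gap. With no events during a lag, exponential times after it and the same median, power at 28 per group is 77.4% for a 2-minute lag, 78.1% for 3 minutes and 80.0% for 5 minutes. The reply adds that the gap is only about 4 points, and about 1 point at 30 per group, and that no source is given for the hazard ratio or the median.

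Much of this stands. The shortfall is conditional, modest and of unknown cause, and it would be wrong to assert that censoring was left out.

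It does not rescue the sentence as written. Reaching 80% at 28 per group needs about 75% control success by 15 minutes. The only success range in the document, in Section 1.0, is 45–70% for pulpal anesthesia in such teeth. A 10-minute median requires at least 50%, and from 50% to 70% power at 28 per group runs from 68.3% to 78.3%. That range is not specific to this regimen, and Section 1.0 also reports better success when articaine infiltration is added, so a higher figure is possible. If the sponsor relied on one, it has to be stated. Nor does enrolling 30 settle the matter, because the plan ties 80% to 28 and reserves the other 2 per group for unusable data.

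**Conclusion.** The concern holds. With exponential times, proportional hazards and the protocol's own 15-minute censoring, power for HR 2.25 is about 76% at 28 per group, not 80%, and about 79% at 30 if all are analyzable. The detectable hazard ratio at 80% power and 28 per group is about 2.34 by formula; simulation at 2.35 confirms 80%. The shortfall of about 4 points disappears if about 75% or more of controls are anesthetized by 15 minutes (Weibull shape of about 1.75 or above). This is a correction to the stated power and its missing assumptions. It does not call the test, the endpoint or the sample size into question.

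**What to change.** Replace the power sentence in Section 11.0 with one that applies the 15-minute limit and names the curve, for example:

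> With 28 evaluable subjects per group, exponential times and censoring at 15 minutes (about 43 expected events), the study has about 76% power to detect a hazard ratio of 2.25, or 80% power to detect a hazard ratio of about 2.35.

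If the calculation used a different control curve, state that instead, together with the PASS procedure, the follow-up time entered and the proportion of controls expected to be anesthetized by 15 minutes. Check that these agree with the 15-minute censoring.

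The cost is one sentence and, in the first case, a slightly less favorable figure. No patients, procedures or data items change.
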